4.0 STUDY DESIGN**4.1 Purpose**

The purpose of this study is to assess prospectively at 6 months the percentage of responder patients implanted with a CRT-D device and a Quartet™ LV quadripolar lead and with the MultiPoint™ Pacing (MPP) feature activated.

A substudy will be carried on in [REDACTED] centers with the intention to assess the acute hemodynamic improvement in patients implanted with a CRT-D device and a Quartet™ LV quadripolar lead and with the MultiPoint™ Pacing (MPP) feature activated.

4.2 Study Design and Scope

This is a post-marketing, prospective, non-randomized, multicenter, regional study. Data will be collected at Enrollment, Baseline, Implant and 6 Month Follow-Up. Additionally, approximately [REDACTED] will participate in a substudy, so additional data will be collected at Substudy Visit within a window of 7 days after the implant.

**CIP**

During the Enrollment visit, the Informed Consent Procedure will be performed and the Inclusion/Exclusion criteria verified. During the Baseline Visit, the Demographic data, Medical History and Cardiac Medication will be collected. Echocardiography measurements during intrinsic rhythm will be collected following the specific study Echocardiography protocol and will be evaluated by an Echo Core Lab. At Implant procedure data and MPP activation evaluation will be collected.

All patients will begin their CRT treatment with the MPP feature turned ON. For those patients who are not able to implant the Quartet™ LV lead or not able to activate the MPP feature, a Termination will be done and their participation in the study will be concluded.

During the Substudy visit, an additional Echocardiography will be performed to [REDACTED] patients [REDACTED] centers. This Echocardiography will not be sent/uploaded to the Echo Core Lab but evaluated locally at hospital.

During the 6 Month visit, clinical and Echocardiography data will be collected. The Echo Core Lab will analyze the data to assess the percentage of responder and non-responder patients. The patient's response to CRT will be evaluated according to LVESV reduction. Patients with a LVESV reduction in MPP compared with the data collected at baseline in No pacing of at least 15% will be classified as Responders.

[REDACTED]

[REDACTED]

4.2.1 Number of subjects required to be included in the study**4.2.2 Estimated time needed to enroll this subject population**

4.3 Objectives

To assess prospectively the changes in left ventricular function at 6 months in patients with the MultiPoint™ Pacing (MPP) feature activated.

4.3.1 Primary Objective

The primary objective of the study is to assess prospectively the percentage of responder patients at 6 months with the MultiPoint™ Pacing (MPP) feature activated.

4.3.2 Secondary Objective

To assess the impact of MPP feature on patient's functional and clinical status.

4.3.3 Substudy Objective

The objective of the substudy is to assess the percentage of patients who achieve a greater hemodynamic response, measured by Cardiac Output, with a MPP configuration or Single Point Pacing (SPP) compared to No Pacing within 7 days after implant.

4.4 Endpoints

4.4.1 Primary Endpoint

The primary endpoint of the study is to measure prospectively at 6 months the percentage of responder patients implanted with a Quartet™ LV quadripolar lead and with the MultiPoint™ Pacing feature activated (using the electrical delay programing approach or anatomical approach) compared with No Pacing at baseline.

A positive CRT response is defined as an improvement of >15 % in Left Ventricular End Systolic Volume (LVESV) at 6 months post-implant, measured by Echocardiography.

4.4.2 Secondary Endpoint

The secondary endpoints of this study are:

- Reverse LV remodeling, measured as changes in LVESV, Left Ventricular End Diastolic Volume (LVEDV), Left Ventricular End Systolic Diameter (LVESD), Left Ventricular End Diastolic Diameter (LVEDD) and Left Ventricular Ejection Fraction (LVEF) at 6 months with MPP compared with no pacing at Baseline
 - Comparison of the above mentioned echo parameters with the patient cohort stratified by etiology (ischemic versus non ischemic patients)
- Percentage of super-responders** at 6 months in MPP
- Dyssynchrony measured by the strain rate (speckle tracking echocardiography) between the anteroseptal segment and the posterior wall (if available)

CIP

- LV lead position
 - Short axis (posteriorolateral, lateral, anterolateral)
 - Long axis (apical, mid-ventricular, basal)
- NYHA class changes at 6 months
- All-cause mortality at 6 months
- All-cause, cardiovascular and/or heart failure hospitalization rate at 6 months
- Combined endpoint of mortality and heart failure hospitalization at 6 months
- Combined endpoint of mortality and cardiovascular hospitalization at 6 months

**Super-responder is defined as a patient with a mean absolute LVEF increase of >14% at 6 months post-implant compared with No Pacing at Baseline.

4.4.3 Substudy Endpoint

The endpoint of the substudy is to assess the percentage of patients who achieve the greater CO improvement with a MPP configuration and/or SPP configuration compared to No Pacing. The CO, based on Velocity Time Integral value (VTI by echocardiography) will be measured within 7 days after implant to evaluate the greater improvement in CO with the following configurations:

- MPP Anatomical approach: choose the most anatomically separated vectors according to fluoroscopy images.
- MPP Electrical approach: choose the most electrically separated vectors according [REDACTED]
- Single Point Pacing: choose the vectors LV1 and LV2 of the approach with the best CO
 - SPP with LV1
 - SPP with LV2

Versus

- NO pacing

4.5 Inclusion and Exclusion Criteria

A subject, who meets all of the inclusion criteria, and none of the exclusion criteria, is eligible to participate in this study. Those patients who agree to participate in the substudy at the selected centers will be candidates for being included in the substudy.

4.5.1 Inclusion Criteria

To participate in this clinical study, the subject must meet all of the following inclusion criteria:

- Patients that will be implanted with a CRT-D with the MultiPoint™ Pacing (MPP) feature under the current ESC or ACCF/AHA/HRS Class I or Class IIa indications for CRT-D implant (including upgrades from single or dual chamber ICD or PM).
- Patient that will be implanted with a Quartet™ Left Ventricular (LV) quadripolar lead.
- In sinus rhythm at baseline visit.
- Patients with Left Bundle Branch Block (LBBB)

**CIP**

- Older than 18 years
- Must be willing and able to comply with study requirements.
- Must indicate their understanding of the study and willingness to participate by signing an appropriate informed consent form.

4.5.2 Exclusion Criteria

Subjects are not eligible for clinical study participation if they meet any of the following exclusion criteria:

- Already has a CRT device implanted.
- Myocardial Infarction or unstable angina within 40 days prior the enrollment.
- NYHA Class IV
- Recent cardiac revascularization (PTCA, Stent or CABG) in the 4 weeks prior to enrollment.
- Cerebrovascular Accident (CVA) or Transient Ischemic Attack (TIA) in the 3 months prior the enrollment.
- Classification of Status 1 for cardiac transplantation or consideration for transplantation over the next 12 months.
- Primary valvular disease requiring surgical intervention.
- Atrial Fibrillation (AF):
 - Persistent AF at the time of enrollment or 30 days prior the enrollment.
 - Permanent AF not treated with AV node ablation within 2 weeks after the CRT-D implant
 - History or incidence of Paroxysmal or Persistent AF within 30 days prior the enrollment
- Patient for whom suitable transthoracic echocardiographic images for determining the cardiac output and LV volumes cannot be obtained.
- Undergone a cardiac transplantation or being waiting for it
- Life expectancy < 6 months
- Pregnancy or planning to become pregnant
- Unable to comply with the follow up schedule
- Currently participating in any other clinical investigation.

4.5.3 Substudy Inclusion Criteria

To participate in the substudy the subject must meet the following inclusion criteria:

- Patients enrolled in the Quarto III Study from the centers participating in the substudy.

4.5.4 Substudy Exclusion Criteria

Subjects are not eligible for the substudy if they meet the following exclusion criteria:

- The patient is not in sinus rhythm in the moment of the substudy visit.

4.6 Subject Population

4.6.1 Subject Screening

All subjects presented at the investigational site can be screened by a member of the investigational team previously trained on the CIP and delegated to do so.

Subjects who do not meet the inclusion/exclusion criteria will not be eligible to participate in this study.

Subjects meeting the inclusion/exclusion criteria will be fully informed about the study and asked to participate in the study. In case the subject agrees, a duly signed and dated Patient Informed Consent will be obtained.

Once the eligible subject has signed the Informed Consent and completed the Baseline visit, he/she will advance to the Implant Procedure visit in which the CRT-D device implant and MPP activation tests will be performed. Depending on the result of this test, the subjects will be classified as:

- **Implant Failure:**

Patients who provided the Informed Consent, meet the Inclusion/Exclusion criteria, but do not receive the CRT-D MPP compatible device or LV lead because of implant failure or physician's decision. These patients' participation into the study will be terminated immediately.

- **MPP Activation Failure:**

Patients who provided the Informed Consent, meet the Inclusion/Exclusion Criteria, have been implanted with a CRT MPP compatible device but not enough MPP vector combinations are possible to allow the MPP activation or the investigator decided not to program the MPP feature ON. These patient's participation to the study will be terminated immediately.

- **Valid subject:**

Patients who provided the Informed Consent, meet the Inclusion/Exclusion criteria, have been implanted with a CRT MPP compatible device, have enough MPP vector combinations to allow the MPP activation and the MPP feature is programmed ON. These patients will proceed in the study and constitute the Study Population.

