**CIP**

withdraw from the study. All reasonable efforts should be made to retain the subject in the clinical study until completion of the study.

Reasons for subject's withdrawal include, but are not limited to:

- Subject refuses to continue participating in the study
- Subject does not meet the inclusion/exclusion criteria and does not require additional follow-up for safety reasons.
- Subject is deceased (cause must be documented)
- Subject's non-compliance
- Subject's participation is terminated by the PI or investigator, although the subject consented, since participation is no longer medically appropriate
- Subject is 'lost to follow up': Subject does not adhere to the scheduled follow up visits but has not explicitly requested to be withdrawn from the clinical study. (This does not apply to missed visits). Site personnel should at all times make all reasonable efforts to locate and communicate with the subject in order to achieve subject compliance to the scheduled follow up visits:
 1. A subject will be considered 'Lost to Follow Up' after a minimum of 2 phone calls of a physician or delegate at the investigational site to the subject or contact. These 2 phone calls need to be documented in the subject's hospital records.
 2. If these attempts are unsuccessful, a letter should be sent to the subject's last known address or general practitioner (GP) and a copy of this letter should be maintained in the subject's hospital records.

Note: If a subject misses one or more of the scheduled follow up visits (inclusive of the assigned visit windows), this will be considered as a missed visit. The subject may therefore still return for subsequent visits and will not be excluded from the study.

If a subject withdraws from the clinical study, the site will record the subject's reasons for withdrawal, on a Termination CRF.

When subject withdrawal from the clinical study is due to an adverse event the subject will be followed until resolution of that adverse event or determination that the subject's condition is stable. The status of the subject's condition should be documented at the time of withdrawal.

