8.1.5.2 Anticipated Serious Adverse Device Effect (ASADE)

A serious adverse device effect which by its nature, incidence, severity or outcome has been previously identified in the risk analysis report.

8.2 Procedure for assessing, recording and reporting adverse events, adverse device effects, serious adverse events and serious adverse device effects:

Safety surveillance within this study and the safety reporting both performed by the investigator, starts as soon as the subject is enrolled in this study (date of signature of the informed consent). The safety surveillance and the safety reporting will continue until the last investigational visit has been performed, the subject is deceased, the subject/investigator concludes his participation into the study or the subject/investigator withdraws the subject from the study, except as otherwise specified in the CIP.

All adverse event data including deaths will be collected throughout the clinical study and will be reported to the Sponsor through the EDC system. The Investigator will record all adverse events and device deficiencies on the appropriate case report forms.

Records relating to the subject's subsequent medical course must be maintained and submitted (as applicable) to the Sponsor until the event has subsided or, in case of permanent impairment, until the event stabilizes and the overall clinical outcome has been ascertained. Adverse events will be monitored until they are adequately resolved. The status of the subject's condition should be documented at each visit.

The investigator will report the event to the IRB/EC per their reporting requirements.

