8.3 Subject Death

8.3.1 Procedure for recording and reporting subject death

All subject deaths are to be documented and reported to the sponsor within 24 hours after becoming aware of the event.

The timing of the Death will be classified as:

- Pre-procedure Death (before the Implant/procedure)
- Peri-Procedure Death (within <=30 days of the implant/procedure)
- Post-Procedure Death (within >30 days after implant/procedure)

Should death occur, the investigator is requested to record death information in the hospital records and immediately document the information on the Death form. By completing the form the sponsor will be notified.

In case of EDC failure, notify Sponsor via [contact] or via Fax (please refer to the Investigator Site Binder, section “Sponsor Contact Details” for further details about Fax numbers).

Patient Death can be an outcome of a serious adverse event (SAE) or serious adverse device effect (SADE).

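### After a failed implant or failed MPP activation, new safety events are no longer collected, so 30-day deaths are incomplete for attempted implants and 6-month event endpoints cover valid subjects only

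*Combined protocol and SAP*

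**What the plan says.** Section 4.6.2 counts a subject as enrolled from written consent, which precedes the implant. Section 4.6.1 then sorts enrolled subjects into three groups after the implant visit.

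- **Implant failure:** subjects who "do not receive the CRT-D MPP compatible device or LV lead because of implant failure or physician's decision". The rule is: "These patients' participation into the study will be terminated immediately".
- **MPP activation failure:** the system is implanted, but there are too few usable vectors or the investigator chooses not to switch MPP on. The rule is: "These patient's participation to the study will be terminated immediately".
- **Valid subject:** implanted, with MPP on. "These patients will proceed in the study and constitute the Study Population".

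Section 4.2 repeats the rule ("a Termination will be done and their participation in the study will be concluded"), and section 6.2 says that subjects without MPP switched on are excluded.

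Under section 8.2, safety surveillance starts at consent. Among the events that end it is that "the subject/investigator concludes his participation into the study or the subject/investigator withdraws the subject from the study", unless the plan specifies otherwise. Section 8.3.1 classifies deaths by timing, including "Peri-Procedure Death (within <=30 days of the implant/procedure". Section 4.4.2 lists all-cause mortality, hospitalization and two combined endpoints at 6 months as secondary endpoints.

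**The concern.** The plan treats the implant as covered by safety surveillance and sets a 30-day window for attributing deaths to it. It then stops observing two groups of subjects at, or very soon after, the procedure. Activation failures leave with the device and lead in place. Section 3.3 lists anticipated complications such as infection, erosion, endocarditis and lead dislodgment, which need not be evident on the implant day.

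Two things are at stake. A count of peri-procedure deaths would look complete for everyone in whom an implant was attempted, but would not be. And 6-month mortality and hospitalization could be read as outcomes of all enrolled subjects when only valid subjects were observed. This is separate from the responder analysis.

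**Working it through.** There is no figure in the plan to reproduce: the sample size, responder rates and dropout allowance are redacted, and no failure rate is given. The check is first a reading of the rules together, then an illustration on assumed values.

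**What is and is not collected**

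1. *Are failures enrolled?* Yes. Enrolment is at consent (4.6.2), and surveillance starts then (8.2).
2. *Are events up to termination collected?* Yes. Table 1 in section 6.2 provides for adverse event, hospitalization and death reporting at the implant visit.
3. *Are events already recorded followed?* Yes. Section 8.2 requires follow-up of recorded events until they settle, whatever the reason for leaving. Section 6.12 adds: "When subject withdrawal from the clinical study is due to an adverse event the subject will be followed until resolution of that adverse event".
4. *Are events that begin after termination collected?* No. Surveillance ends with participation (8.2), and the exception clause there finds no matching provision for these groups in 4.2, 4.6.1, 6.2 or 6.12. No later contact is scheduled.
5. *Does the analysis section repair this?* No. Section 12.1 applies intention-to-treat to the primary endpoint only, section 12.10 rules out imputation, and no safety analysis set is defined.

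The gap is therefore new-onset events after termination.

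**Illustration of size (all inputs assumed)**

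Let f be the share of subjects terminated as failures, r their event risk relative to valid subjects, and c the share of their events captured before or despite termination.

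- Relative understatement of risk if only valid subjects are counted: 1 − 1/(1 + f(r − 1)).
- Share of all events missed: (1 − c)·f·r / (1 − f + f·r).

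Example with f = 10%, r = 3: f·r = 0.30 and 1 − f + f·r = 1.20. The share missed is 0.30/1.20 = 25.0% with c = 0 and 12.5% with c = 0.5. The understatement is 1 − 1/1.20 = 16.7%.

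| f | r | Risk understated by | Events missed, c = 0 | Events missed, c = 0.5 |
|---|---|---|---|---|
| 5% | 1 | 0% | 5.0% | 2.5% |
| 5% | 2 | 4.8% | 9.5% | 4.8% |
| 5% | 3 | 9.1% | 13.6% | 6.8% |
| 10% | 1 | 0% | 10.0% | 5.0% |
| 10% | 2 | 9.1% | 18.2% | 9.1% |
| 10% | 3 | 16.7% | 25.0% | 12.5% |
| 15% | 1 | 0% | 15.0% | 7.5% |
| 15% | 2 | 13.0% | 26.1% | 13.0% |
| 15% | 3 | 23.1% | 34.6% | 17.3% |

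At r = 1 the rate in valid subjects is unbiased, but events are still lost from the count.

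**The case against.** The strongest reply is that the restriction fits the question. This is a post-market study of CE-marked devices in patients already indicated for CRT. Its secondary objective concerns the effect of MPP, and subjects without MPP cannot inform it. The 30-day category is a timing label for reported deaths, not an endpoint or a rate, and section 4.6.1 says openly who forms the study population. Section 8.3.1 also asks sites to report subject deaths once they learn of them.

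Much of this stands. Limiting the 6-month endpoints to valid subjects is defensible if it is stated. It does not close the gap before day 30: the label is anchored to the procedure, which failures with an attempted implant also undergo, and reporting on awareness without any scheduled contact leaves capture to chance.

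The reply also rules out several stronger readings that a reader might infer:

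- *That complications seen at the procedure are lost.* They are reportable, and they are followed to their outcome under section 8.2 whether or not they caused the withdrawal.
- *That the 30-day category cannot be filled at all for failures.* Deaths during the procedure, and deaths from an event already recorded, can be placed in it.
- *That a device-event endpoint is compromised.* Section 4.4 lists none; device effects appear only in the safety reporting of section 8.
- *That the unobserved subjects are those most exposed to procedural harm.* The documents do not show this. Both groups include discretionary decisions, and a valid subject is defined by device, vectors and programming, not by an uneventful procedure.

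**Conclusion.** The point holds as a gap in data collection. Deaths, hospitalizations, and serious or device-related events that begin after termination are not collected for failed-implant and failed-activation subjects, although they are enrolled. The peri-procedure death category is therefore incomplete for attempted implants, and the 6-month mortality and hospitalization endpoints describe valid subjects only.

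The conclusion rests on the text alone. Its size cannot be derived from the documents. The tabulated 2.5% to 34.6% of events missed, and the 0% to 23.1% understatement of risk, depend wholly on the assumed failure share, relative risk and capture. They show that the gap could matter, not that it does. In particular, a claim that the reported rates will be too low needs r above 1, which the documents neither state nor test. The change is worth making because it is cheap, improves safety capture, and leaves the primary endpoint and clinical care untouched.

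**What to change.** Amend sections 4.6.1 and 8.2, with matching text in 4.2 and 6.2, so that implant or activation failure ends efficacy participation only. Continue adverse-event and vital-status data collection to day 30 after the procedure for every subject with an attempted implant, by one phone or chart contact. Define an attempted implant as a procedure that was begun, so that a decision not to start is not counted as one.

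Report deaths, SAEs/SADEs and hospitalizations to day 30 for all attempted implants. Label the 6-month mortality, hospitalization and combined endpoints in section 4.4.2 as applying to valid subjects, and give the number of implant and activation failures beside them.

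The cost is one extra contact for what should be a small group and a change to the protocol and consent wording. The safety figures may also be slightly less favourable.

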4.6.2 Point of Enrollment

Subjects are considered enrolled in the study from the moment the subject has provided written Patient Informed Consent, prior to the CRT-D implant. (Refer to the following Section for the Informed Consent Process).

